Information on subject satisfaction and leg wound complications will be obtained at discharge and six weeks post-CABG. Local site coordinators will contact the subjects every three months to collect information by phone regarding the subject's health status throughout the active follow-up .

Subjects will be encouraged to seek medical attention as instructed upon discharge from the hospital. All efforts will be made to obtain follow-up information on subjects who have visited a hospital, underwent procedures or have been treated for serious adverse events in a non-study-related hospital(s). Non-study hospital related materials will be collected and reviewed at the study coordinating centers.

Throughout the duration of the study participation, the subject will be encouraged to maintain a point of contact with the local site investigator and the study coordinator for research related activities and questions. The study team at each site will maintain a dedicated point of contact for all subjects seeking information during their study participation. The study coordinator at each site will communicate any necessary medical information to the surgeon investigator and the clinical care team.

Long-term secondary MACE outcomes will be collected by passive follow-up using VA databases for an additional two years after the completion of the active follow-up phase.

C. Protocol Non-compliance

Any protocol non-compliance will be reported immediately to the Chairman's office and the Perry Point CSPCC. Each of these groups then reserves the right to forward notification, as required by local policy and regulation. Examples of protocol non-compliance include failure to obtain informed consent, failure to adhere to exclusion criteria, failure to report a serious adverse event, or no surgery is performed after randomization etc.

D. Site Performance Monitoring

In order to assure the successful conduct and completion of this study, all sites must adhere to certain performance standards. The Perry Point CSPCC and the Chairman's Office will jointly set performance standards and monitor site activities to assure that these standards are met.

All cooperative studies are on probation during the first year of enrollment. Studies that do not recruit at least 90% of the target enrollment during the first year are in danger of having monetary support stopped.

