1-2 times per week.....	
Less than once a week	
None over the past 4 weeks	

VISIT NO.

--	--

SITE NO.

--	--	--

SUBJECT ID

--	--	--	--

ALPHA CODE

--	--	--	--

5. How bothersome is it for you to take your pills for chest pain, chest tightness or angina as prescribed?

Extremely bothersome

Quite a bit bothersome

Moderately bothersome

Slightly bothersome

Not bothersome at all

My doctor has not prescribed pills

6. How satisfied are you that everything possible is being done to treat your chest pain, chest tightness, or angina?

Not satisfied at all

Mostly dissatisfied

Somewhat satisfied

Mostly satisfied

Completely satisfied

7. How satisfied are you with the explanations your doctor has given you about your chest pain, chest tightness, or angina?

Not satisfied at all

Mostly dissatisfied

Somewhat satisfied

Mostly satisfied

Completely satisfied

VISIT NO.

--	--

SITE NO.

--	--	--	--

SUBJECT ID

--	--	--	--	--

ALPHA CODE

--	--	--	--	--

8. Overall, how satisfied are you with the current treatment of your chest pain, chest tightness, or angina?

Not satisfied at all.....

Mostly dissatisfied ..

Somewhat satisfied ..

Mostly satisfied ..

Completely satisfied ..

9. Over the past 4 weeks, how much has your chest pain, chest tightness, or angina limited your enjoyment of life?

It has extremely limited my enjoyment of life ..

It has limited my enjoyment of life quite a bit ..

It has moderately limited my enjoyment of life ..

It has slightly limited my enjoyment of life ..

It has not limited my enjoyment of life at all ..

10. If you had to spend the rest of your life with your chest pain, chest tightness, or angina the way it is right now, how would you feel about this?

Not satisfied at all.....

Mostly dissatisfied ..

Somewhat satisfied ..

Mostly satisfied ..

Completely satisfied ..

VISIT NO.

--	--

SITE NO.

--	--	--

SUBJECT ID

--	--	--	--

ALPHA CODE

--	--	--	--

11. How often do you think or worry that you may have a heart attack or die suddenly?

I can't stop thinking or worrying about it

I often think or worry about it.....

I occasionally think or worry about it.....

I rarely think or worry about it.....

I never think or worry about it.....

VISIT NO.	SITE NO.	SUBJECT ID	ALPHA CODE	DATE OF ASSESSMENT														

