2 STUDY OBJECTIVES AND ENDPOINTS

2.1 Study Objectives and Hypotheses

Primary Objectives:

Objective 1: To investigate the impact of SVG harvesting techniques – OVH vs. EVH on MACE, a composite end point of all-cause mortality, nonfatal myocardial infarction and repeat revascularization, over the active follow-up period of the study postoperatively.

Hypothesis 1: A significantly smaller proportion of CABG subjects with SVGs harvested by open technique will experience MACE post-surgery compared to CABG subjects with SVGs harvested by endoscopic technique during the active follow-up period.

Secondary Objectives:

Objective 2: To investigate the impact of SVG harvesting techniques – OVH vs. EVH on MACE, a composite endpoint of all-cause mortality, nonfatal myocardial infarction and repeat revascularization, at one and three-year postoperatively.

Hypothesis 2: One-year composite MACE rate will be 6 percentage points lower in the open harvesting group and three-year composite MACE rates will be at least 8-10 percentage points lower in the open vein harvesting group compared to the endoscopic vein harvesting group.

Objective 3: To investigate the impact of SVG harvesting techniques – OVH vs. EVH on MACE, a composite endpoint of all-cause mortality, nonfatal myocardial infarction and repeat revascularization, over the entire follow-up period (active and passive) of the study postoperatively.

Hypothesis 3: A significant smaller proportion of CABG subjects with SVGs harvested by open technique will experience MACE post-surgery compared to CABG subjects with SVGs harvested by endoscopic technique during the entire follow-up period.

Tertiary Objectives:

Objective 4: Investigate the impact of the two harvesting techniques - open vs. endoscopic - on clinical indicators of leg wound complications and subject satisfaction at six weeks post-surgery.

Hypothesis 4: Leg wound complications will be lower and satisfaction will be higher in the EVH group compared to OVH group.

Objective 5: Compare subject quality of life scores according to the SVG harvest technique at six weeks post-surgery.

Hypothesis 5: Subjects' quality of life scores will be higher in the EVH group compared to the OVH group.

Objective 6: Determine the role of vein harvester experience on clinical outcomes.

Exploratory Aim with no hypothesis specified.

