2.3 Derived variables

2.3.1 Seattle Angina Questionnaire

The Seattle Angina Questionnaire (SAQ) is the leading health-related QoL measure for patients with coronary artery disease. The self-assessment questionnaire consists of a list of activities people often do during the week (e.g., dressing yourself, walking indoors on level ground, showering) and asks participants the amount of limitation (ranging from not at all limited to extremely limited) they have doing these activities due to chest pain, chest tightness, or angina over the previous 4 weeks. Additional questions ask about frequency and treatment of chest pain, chest tightness, or angina.

The answers provided on the SAQ are used to calculate scores in five scales: 1) Angina Stability, a measure of whether a patient's symptoms are changing over time; 2) Angina Frequency, a measure of how often a patient is having symptoms now; 3) Physical Limitation, a measure of how much a patient's condition is hampering his ability to do what he wants to do; 4) Treatment Satisfaction, a measure of well a patient understands her care and what she thinks of it; and 5) Quality of Life, a measure of the overall impact of a patient's condition on a patient's interpersonal relationships and state of mind. Participants will complete the SAQ at baseline, 6 weeks, and 1 year post-surgery. Higher scores are better. For follow-up assessments, participants will be categorized as "improved", "no change", or "worsened" based on their baseline scores.

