7.3 Tertiary Outcomes

Tertiary objectives of this study include investigating the impact of SVG harvesting techniques – OVH vs. EVH on leg wound complication, patient satisfaction, and quality of life in addition to determining the role of vein harvester's experience on clinical outcomes.

All participants will be examined for post-operative complications of the leg wound from harvesting at discharge and at six weeks post-surgery. Post-operative leg wound complication status (yes-1/no-0) will be determined. The proportion of participants with leg wound complications will be computed for each treatment group and these proportions will be compared using Pearson's chi-square test (TABLE 27). The impact of confounding variables, such as BMI, diabetes status, and smoking status, on post-operative leg wound infection will be analyzed using multivariable logistic regression (TABLE 28). Surgical site infections at the vein harvest site according to the Center for Disease Control criteria will be explored.

Patient satisfaction will be assessed using the "Treatment Satisfaction" scale of the Seattle Angina Questionnaire. Participants will be categorized as "improved", "no change" and "worsened" at 6 weeks and 12 months compared to their baseline scores (TABLE 29). The proportion of participants in these three categories will be compared between the two groups using Pearson's chi-square test. The actual scores from these measures will also be used to compare harvesting techniques using analysis of covariance (ANCOVA) techniques, where the baseline (pre-surgery) scores will be used as a covariate (TABLE 30).

The occurrence of severe leg pain, due to incisions made during vein grafting, will be collected at discharge and 4-6 weeks post-CABG. The proportion of participants with severe pain (yes = pain severity rating score ≥ 3) at each time point will be compared across groups using Pearson's chi-square test (TABLE 31).

Quality of life scores using the PCS and MCS of the VR-12 and the "Quality of Life" scale of the Seattle Angina Questionnaire will be computed at baseline, six weeks, and 12 months post-surgery for participants in each SVG harvesting group. For each component of the VR-12 (PCS and MCS), mean changes from baseline at six weeks and 12 months will be computed and compared using ANCOVA (TABLE 32).

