For each scale of the SAQ (angina stability, angina frequency, physical limitation, treatment satisfaction, & quality of life), participants will be categorized as “improved”, “no change” and “worsened” at 6-weeks and 12 months compared to their baseline scores (TABLE 29). The proportion of participants in these three categories at each time point will be compared between the two groups using Pearson's chi-square test. The actual scores from these measures and that of the VR-12 MCS and PCS will be used to compare harvesting techniques using ANCOVA techniques, where the baseline (pre-surgery) scores will be used as a covariate (TABLE 30).

The hypotheses for the tertiary aims of this study are:

H4: Leg wound complications will be lower and satisfaction will be higher in the EVH group compared to OVH group.

H5: Subjects' quality of life scores will be higher in the EVH group compared to the OVH group.

H6: Exploratory Aim with no hypothesis specified.

The leg wound complication component of hypothesis H4 will be supported when the percent of participants experiencing leg wound complications randomized to EVH is lower than that of participants randomized to OVH with a significant *p*-value observed. Higher patient satisfaction in the EVH group vs. OVH group will be supported by a significant effect for treatment when entered into the ANCOVA model and a positive coefficient for EVH vs. OVH. The hypothesis H5 will be supported by a significant effect for treatment when entered into the ANCOVA model and a positive coefficient for EVH vs. OVH for the outcomes of SAQ quality of life scale, VR-12 PCS, and VR-12 MCS.

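### The satisfaction part of H4 is decided by an angina-care scale that asks nothing about the leg or the vein harvest

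*SAP*

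**What the plan says.** H4 in SAP 2.1 reads "Leg wound complications will be lower and satisfaction will be higher in the EVH group compared to OVH group". Its objective, in SAP 2.1 and in Protocol III (other objectives, item 1), pairs satisfaction with leg wound complications at six weeks.

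SAP 7.3 names the instrument: "Patient satisfaction will be assessed using the" Treatment Satisfaction scale of the SAQ. The score is classed as improved, unchanged or worsened against baseline, and is also analysed by ANCOVA with the pre-surgery score as covariate. The decision rule is explicit: "Higher patient satisfaction in the EVH group vs. OVH group will be supported by a significant effect for treatment when entered into the ANCOVA model", together with a positive coefficient for EVH.

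The protocol describes the collection of satisfaction data differently. Under XI.B Subject Management: "Information on subject satisfaction and leg wound complications will be obtained at discharge and six weeks post-CABG". Under X.A Six Week Visit it mentions a self-completed satisfaction survey in addition to the quality-of-life questionnaires.

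**The concern.** H4 concerns what patients gain from a smaller leg wound. The SAQ is about angina. If the scale contains nothing on the harvest, the test answers a different question from the one in the hypothesis, whatever its p-value.

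The plan nevertheless turns that p-value into a statement about H4. A null result would be read as no satisfaction benefit from EVH, and a positive one as patients preferring EVH. The scale could also move against EVH for reasons unrelated to the leg. The primary hypothesis is that EVH leads to more MACE, including repeat revascularization, and graft problems of that kind could lower satisfaction with angina care even in patients pleased with the small incision.

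**Working it through.** No arithmetic applies, because the documents give no sample size, power or effect size for satisfaction. The check sets the hypothesis, the questions patients answer and the schedule side by side.

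1. **What satisfaction means in H4.** The objective pairs it with leg wounds. Protocol I lists satisfaction beside wound morbidity, pain and cosmetic result when describing the short-term results of EVH. Protocol VII.A says that the morbidity of open harvest reduces satisfaction. The natural reading is satisfaction related to the harvest.

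2. **What Form 03 asks.**

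| Item | Subject |
|---|---|
| 1–4 | Activity limits, change in symptoms, frequency, nitroglycerin use, all tied to chest symptoms |
| 5 | "How bothersome is it for you to take your pills for chest pain, chest tightness or angina as prescribed" |
| 6 | "How satisfied are you that everything possible is being done to treat your chest pain, chest tightness, or angina" |
| 7 | "How satisfied are you with the explanations your doctor has given you about your chest pain, chest tightness, or angina" |
| 8 | Overall satisfaction with current treatment of chest symptoms |
| 9–10 | Enjoyment of life, and feelings about living on with the chest symptoms |
| 11 | Worry about heart attack or sudden death |

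   Items on the leg, incision, scar or harvest: 0 of 11. Items 6, 7, 8 and 10 offer answers graded by satisfaction, and each refers to chest symptoms or angina. The documents do not say which items make up the Treatment Satisfaction scale. Items 5–8 are the likely set by content, but the count of 0 of 11 makes the conclusion independent of that choice.

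3. **The baseline score.** SAP 7.3 measures change from a pre-surgery score. Satisfaction with angina care exists before surgery; satisfaction with a harvest does not. The planned analysis fits the first construct and not the second.

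4. **Whether another form fills the gap.** Protocol Table 2 and SAP Table 1 list no satisfaction survey. Forms 08 and 09 ask about leg incision pain and its impact. Form 10 yields a wound score whose content SAP 2.3.7 describes, with no satisfaction element. The first page of Form 10 and the whole of Form 13 (MACE events) are absent from the text I have, but neither title suggests a satisfaction measure. SAP 2.3.1 gives the SAQ at baseline, six weeks and one year, so nothing matches the discharge time point in Protocol XI.B.

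**The case against.** The best defence is that H4 says only satisfaction, without adding that it is satisfaction with the harvest, and that SAP 2.3.1 describes the scale broadly: "Treatment Satisfaction, a measure of well a patient understands her care and what she thinks of it". Tables 29 and 30 are also titled as SAQ results, so a careful reader would see the source. It stands that the harvest-specific reading is an inference from the objective and the background. But patients answer the wording of the form, which is tied to angina throughout, and SAP 7.3 carries the result into H4 whatever the table title.

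Several stronger readings are tempting and are not supported:

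- **That H4 as a whole cannot be answered.** Its leg-wound part has its own assessment, chi-square test and logistic model (Tables 27 and 28).
- **That satisfaction is the main benefit claimed for EVH.** The protocol lists it among several benefits, and the SAP's own description of EVH (2.3.8) names wound infections and leg wound complications instead.
- **That a positive result would merely reflect angina relief.** Items 6 and 7 ask about the effort of care and the doctor's explanations, so the cause of any difference would be unknown.
- **That the missing discharge assessment defeats the comparison.** Objective 4 is set at six weeks, when the SAQ is given. The discharge statement is a separate inconsistency to reconcile.
- **That leg-pain impact could replace satisfaction.** It is already planned by arm in Table 31, and it measures pain.

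**Conclusion.** The point holds for the satisfaction part of H4 only. As written, the decision rule would let a comparison of satisfaction with angina care support or fail to support a claim about harvest technique, and neither outcome should be reported that way.

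The reach is small: one of two parts of one tertiary hypothesis. No primary or secondary analysis, sample size or safety summary depends on it. It still merits correction before analysis, because the SAP states a rule that would lead to an unsupported conclusion.

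The verdict rests on three assumptions: that satisfaction in H4 means satisfaction related to the harvest, that Form 03 is used as printed, and that no satisfaction form exists outside the two schedules.

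**What to change.** In SAP 7.3, report the SAQ scale only as satisfaction with angina treatment and remove it from the H4 decision rule. Log this as a deviation from the protocol, as Protocol XVII.H requires, since H4 comes from the protocol's objectives. Reconcile Protocol X.A and XI.B with the schedule of forms, so that the satisfaction survey and its discharge and six-week time points either correspond to a form or are withdrawn.

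Then choose one of two courses:

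- **Keep the claim.** Add one question on satisfaction with the leg incision to the six-week Form 09, and compare it between arms without a baseline covariate.
- **Drop the claim.** State that satisfaction with the harvest is not tested, and report the leg-pain impact comparison in Table 31 as a separate outcome.

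The SAP change costs only wording, at the price of a narrower or abandoned satisfaction claim. A new question needs a form amendment and local IRB approval (Protocol XV.A), and would miss participants already past six weeks. SAP Table 3 runs to Month 38 with named centres, which suggests, but does not prove, that recruitment was well advanced. If so, the second course is the realistic one.

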c. Showering						
d. Climbing a hill or a flight of stairs without stopping						
e. Gardening, vacuuming, or carrying groceries						
f. Walking more than a block at a brisk pace						
g. Running or jogging						
h. Lifting or moving heavy objects (e.g. furniture, children)						
i. Participating in strenuous sports (e.g. swimming, tennis)						

VISIT NO.	SITE NO.	SUBJECT ID	ALPHA CODE													

 	 	

			

 	 	 	

				

 	 	 	 	

					

 	 	 	 	

				

2. Compared with 4 weeks ago, how often do you have chest pain, chest tightness, or angina when doing your most strenuous activities? I have had chest pain, chest tightness, or angina

Much more often	
Slightly more often	
About the same	
Slightly less often	
Much less often	
I have had no chest pain over the last 4 weeks	

3. Over the past 4 weeks, on average, how many times have you had chest pain, chest tightness, or angina? I have had chest pain, chest tightness, or angina

4 or more times per day	
1-3 times per day	
3 or more times per week but not every day.....	
1-2 times per week.....	
Less than once a week	
None over the past 4 weeks	

4. Over the past 4 weeks, on average, how many times have you had to take nitroglycerin (nitroglycerin tablets or spray) for your chest pain, chest tightness, or angina?
I have taken nitroglycerin

4 or more times per day	
1-3 times per day	
3 or more times per week but not every day.....	

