Center	Rate of Reporting	Participant ID	Protocol Non-Compliance Code	Date of Deviation
Albuquerque (501)				
...				
... and so on				

FIGURE 2: Kaplan-Meier Survival Curves

[figure not shown]

TABLE 25: MACE, Active Follow-up: Results of Multivariable Cox Proportional Hazards Regression Model

Parameter	DF	Parameter Estimate	Standard Error	Chi-Square Test Statistic	p-value	Hazard Ratio	95% Hazard CI
EVH (vs. OVH)							
Covariate 1							
...							
... and so on							

TABLE 26: Major Adverse Cardiac Events at 1-year and 3-year, by Treatment

		OVH		EVH		Total		p-value
		N	%	N	%	N	%	
1-Year	MACE							
	Death							----
	MI							----
	RR							----
3-Year	MACE							
	Death							----
	MI							----
	RR							----

TABLE 27: Leg Incision Healing by Treatment

	OVH		EVH		Total		p-value
	N	%	N	%	N	%	
No Disturbance							----
Complication (Any Disturbance)							

TABLE 28: Leg Incision Healing by Treatment: Results of Multivariable Logistic Regression Model

Parameter	DF	Parameter Estimate	Standard Error	Chi-Square Test Statistic	p-value	Odds Ratio	95% CI
EVH (vs. OVH)							
Covariate 1							
...							
... and so on							

TABLE 29: Seattle Angina Questionnaire: Change from Baseline by Treatment

			OVH		EVH		Total		p-value
			N	%	N	%	N	%	
[Component scale]	6-week	Improved							
		No Change							----
		Worsened							-----
	12-month	Improved							
		No Change							----
		Worsened							-----

* No change = (mean score change < 5)

TABLE 30: Seattle Angina Questionnaire: Results of ANCOVA Model

		Parameter	DF	Parameter Estimate	Standard Error	t-Test Statistic	p-value
[Component scale]	[6-week /12-month]	Intercept					
		Baseline Score					
		EVH (vs. OVH)					
		Interaction (if needed)					

TABLE 31: Impact and Severity of Incisional Leg Pain at by Treatment

		OVH		EVH		Total		p-value
		N	%	N	%	N	%	
Discharge	Little or no impact (impact score ≤ 50)							
	Some impact ($50 < \text{impact score} \leq 57$)							----
	Substantial impact ($57 < \text{impact score} \leq 63$)							----
	Severe impact (impact score > 63)							----
	Severe (per severity rating) (Score of 3 or above)							
6-Weeks	Little or no impact (impact score ≤ 50)							
	Some impact ($50 < \text{impact score} \leq 57$)							----
	Substantial impact ($57 < \text{impact score} \leq 63$)							----
	Severe impact (impact score > 63)							----
	Severe (per severity rating) (Score of 3 or above)							

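### SAP 7.3 and Table 29 label Angina Stability improved or worsened against baseline although the item already asks for change, and the printed no-change cut-off carries no sign or absolute value.

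*SAP*

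**What the plan says.** SAP 2.3.1 lists five SAQ scales. One is described as "Angina Stability, a measure of whether a patient's symptoms are changing over time"; the next as "Angina Frequency, a measure of how often a patient is having symptoms now". The first is thus a measure of change and the second a measure of current state. The same section gives the direction of scoring: "Higher scores are better".

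Form 03 in the protocol's research data forms contains the questionnaire. Question 2 reads "Compared with 4 weeks ago, how often do you have chest pain, chest tightness, or angina when doing your most strenuous activities", with five ordered answers from *much more often* to *much less often*, and a sixth for no chest pain in the last 4 weeks.

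SAP 7.3 treats the five scales alike: "For each scale of the SAQ (angina stability, angina frequency, physical limitation, treatment satisfaction, & quality of life), participants will be categorized". The labels are improved, no change or worsened, assigned at 6 weeks and 12 months relative to baseline. Pearson's chi-square is the test named in the sentence that follows: "The proportion of participants in these three categories at each time point will be compared between the two groups using" that statistic. ANCOVA is also applied to the actual scores, with the baseline score as covariate.

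The only cut-off is in the footnote to SAP Table 29: "No change = (mean score change < 5". No cut-off is printed for improved or worsened. The protocol's Statistical Analysis Plan section (XVII.D) names three categories and gives no threshold.

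**The concern.** There are two separate defects of definition.

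**Angina Stability.** For a scale that records current state, follow-up minus baseline is a change and the three labels mean what they say. Angina Stability already records change, so subtracting baseline gives a change of a change. A reader of Table 29 will take worsened on this scale to mean worse angina, and it need not mean that.

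**The footnote.** With higher scores better, a decline is a negative number, and every negative number is below 5. A programmer who codes the rule as printed would place all decliners in no change. The footnote also speaks of a mean, although the rule classifies individual participants.

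At stake is the meaning of the category labels in a tertiary table that includes Treatment Satisfaction, the SAP's measure of patient satisfaction.

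**Working it through.** The plan states no numerical result here, so the check is on the rule itself.

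**Which item is Angina Stability.** The documents do not say so outright. Question 2 is the only Form 03 item that asks for a comparison over time, so it is the one that fits the definition in SAP 2.3.1.

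**What each visit compares.** Protocol section X.A places the six-week visit at 4 to 8 weeks after surgery. Four weeks earlier is 4 − 4 = 0 to 8 − 4 = 4 weeks after surgery. At 12 months the item looks back to about month 11. Neither follow-up answer refers to the pre-operative state.

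**Number of comparisons.** 5 scales × 2 visits = 10 chi-square comparisons. Angina Stability supplies 1 × 2 = 2. The footnote governs all 10.

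**Answer pairs for question 2.** Six answers at baseline and six at follow-up give 6 × 6 = 36 pairs. The documents print no SAQ scoring, so three scorings were assumed:

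- A: five ordered answers at 0, 25, 50, 75, 100, with no chest pain at 50.
- B: the same, with no chest pain at 100.
- C: six equal steps, 0, 20, 40, 60, 80, 100.

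Change = follow-up − baseline. The two-sided rule is improved if change ≥ +5, worsened if change ≤ −5, otherwise no change. The printed rule is no change if change < 5. A conflict is a pair labelled worsened when the follow-up answer is *about the same*, less often or no pain, or labelled improved when the follow-up answer is more often.

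| Scoring | Two-sided rule: improved / no change / worsened | Printed rule: no change | Declines that meet the printed rule | Conflicts under two-sided rule |
|---|---|---|---|---|
| A | 14 / 8 / 14 | 8 + 14 = 22 | 14 of 14 | 6 |
| B | 14 / 8 / 14 | 8 + 14 = 22 | 14 of 14 | 6 |
| C | 15 / 6 / 15 | 6 + 15 = 21 | 15 of 15 | 7 |

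**Examples under A.** *Much less often* at baseline, then *slightly less often*: 75 − 100 = −25, worsened, although the patient reports easing at both visits. *Much more often*, then *slightly more often*: 25 − 0 = +25, improved, although the patient reports more angina at both visits.

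**A stricter count.** Someone may regard worsened as fair when the follow-up answer is *about the same*. Removing those pairs leaves 6 − 2 = 4 (A), 6 − 3 = 3 (B) and 7 − 3 = 4 (C). The two examples above remain conflicts under every scoring.

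**What this shows.** Repairing the footnote does not repair the Angina Stability labels, because the conflicts were counted under the two-sided rule. These are counts of possible answer pairs. They do not estimate the share of patients affected, which the documents give no means to estimate.

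**The case against.** The strongest case on the other side has five parts.

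1. *The footnote is plainly two-sided.* Table 29 has its own Worsened row, and SAP 2.3.1 and 7.3 both name three categories. Absolute-value bars may also have been lost in extracting the text from PDF. This stands as to intent: a reader might infer that the SAP plans to count every decliner as unchanged, and the documents do not support that. What remains is that the rule as printed needs a sign and that two of the three cut-offs are not printed.

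2. *The ANCOVA is sound.* A reader might infer that it too analyses a difference of two changes. It does not. It models the follow-up score with a pre-randomization covariate, and under randomization that is a valid comparison between arms even if the covariate predicts poorly. This stands in full.

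3. *The chi-square tests are valid.* A reader might infer that they cannot be interpreted. They remain valid tests of whether the category distribution differs between randomized arms. This stands. The fault lies in what the labels say clinically.

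4. *Worsened could be read as a lower stability score.* That is literally correct, and current symptoms are covered by Angina Frequency. It does not help the reader of a table whose row labels are improved and worsened, when a patient's own answer says the reverse.

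5. *The short recall at six weeks applies to both arms, and other SAQ items also use 4 weeks.* This is true, so recall is not a source of bias between arms. It matters here only because it confirms that the item does not look back to baseline.

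**Conclusion.** The point holds in limited form and is minor. For Angina Stability, 2 of the 10 SAQ category comparisons carry labels that can contradict the patient's follow-up answer: 6 to 7 of 36 possible answer pairs under three assumed scorings, or 3 to 4 on the stricter count. Separately, the no-change rule used in all 10 comparisons is incomplete as printed.

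No hypothesis decision changes. By SAP 7.3, the leg-wound part of H4 is judged on complication proportions, its satisfaction part by ANCOVA on Treatment Satisfaction, and H5 by ANCOVA on SAQ Quality of Life and the VR-12 PCS and MCS. None uses the three categories.

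The conclusion rests on two assumptions: that Form 03 question 2 is the Angina Stability scale, which follows from the SAP's own definition, and that its score rises in order from *much more often* to *much less often*, in line with higher scores being better. The exact scoring alters the counts but not the conclusion.

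**What to change.** - Remove Angina Stability from the improved / no change / worsened categories in SAP 7.3 and Table 29. In its place, tabulate the distribution of answers by arm at each visit, with the no-chest-pain answer as its own row. Its ANCOVA may stay.
- Restate the Table 29 footnote for the other four scales in terms of individual change from baseline, keeping the SAP's own 5 points: improved ≥ +5, worsened ≤ −5, no change = absolute change < 5. Delete the word mean.

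The cost is SAP wording and table-shell edits, with no new data. The one downside is that Angina Stability no longer appears in the same three-category format as the other scales.
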